3. Changes in infant intentional communication. [Measured via a project-developed coding system.] The rationale for including this outcome measure is that parental responsive support of infant engagement will promote infants' increased use of intentional communication, previously found to predict later receptive and expressive language outcomes for preschoolers already diagnosed with autism (Yoder et al., 2015).

The following 8 secondary outcome variables will be measured at two timepoints: Baseline and Posttest 2. For these measures, we are particularly interested in examining the magnitude of change over the course of the full intervention, as well as whether there are order effects (differences between study arms) at Posttest 2.

4. Changes in infant respiratory sinus arrhythmia (RSA). This measure was chosen as an index of parasympathetic system functioning, and will be measured within a paradigm in which the infants are passively observing vignettes of infant-directed speech, as an intended experimental analog of the live parent-infant interactions we are videorecording to derive other outcome measures. We hypothesize we will see increased RSA levels during infant-directed speech, reflecting greater parasympathetic control, by Posttest 2.
5. Changes in infant skin conductance level (SCL). This measure was chosen as an index of sympathetic system functioning, and will be measured within the above described infant-directed speech paradigm. We hypothesize we will see decreased SCL levels during infant-directed speech, reflecting less elevation of sympathetic activity when observing infant-directed speech vignettes, by Posttest 2.
6. Changes in infants' receptive language. [Measured via the Mullen Scales of Early Learning (MSEL) Receptive Language scale, Mullen, 1995.] This measure is a more distal outcome measure that we hypothesize will improve in association with improvements in parent-infant dyadic engagement and infant intentional communication.
7. Changes in infants' expressive language. [Measured via the MSEL Receptive Language scale, Mullen, 1995.] This measure also is a more distal outcome measure that we hypothesize will improve in association with improvements in parent-infant dyadic engagement and infant intentional communication.

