3. Changes in infant intentional communication. [Measured via a project-developed coding system.] The rationale for including this outcome measure is that parental responsive support of infant engagement will promote infants' increased use of intentional communication, previously found to predict later receptive and expressive language outcomes for preschoolers already diagnosed with autism (Yoder et al., 2015). Intentional communication acts are defined as acts that are directed toward a communication partner (in this case, the parent or other primary family caregiver present during the parent-infant interaction session) to convey a message, and include (a) vocalizations, (b) gestures, or (c) combinations of both vocalizations and gestures. A coding manual will be developed to describe the coding system and provide examples and nonexamples of Infant intentional communication acts. This measure will be coded from videos of the parent-infant interaction sessions. Research assistants will be trained to reliability by supervising project staff. One of every five coded videos will be randomly selected for independent coding by another research assistant. Coders will be blind to assigned arm of the intervention and to timepoint of the assessment.

The following 8 secondary outcome variables will be measures at two timepoints: Baseline and Posttest 2. For these measures, we are particularly interested in examining the magnitude of change over the course of the full intervention, as well as whether there are order effects (differences between study arms) at Posttest 2.

4. Changes in infant respiratory sinus arrhythmia (RSA). This measure was chosen as an index of parasympathetic system functioning, and will be measured within a paradigm in which the infants are passively observing (a) an instrumental music video without social images, and (b) three on-minute vignettes of infant-directed speech, as an experimental analog of parent-infant interactions. We hypothesize we will see increased RSA levels during infant-directed speech, reflecting greater parasympathetic control and improved

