6.4.2 Sample Size Considerations

Assuming recruitment of 44 infant-parent dyads and allowing for a 9% (n=4) dropout rate, which is consistent with high retention rates (> 95%) in our prior intervention studies, 40 dyads (20 per treatment arm) will have complete data for analyses. Assuming a conventional type I error rate of .05, and intercorrelations among the repeated measures from .3 to .7, the magnitude of treatment group effects detectable with a .80 statistical power will range from $f=.37$ to $.42$, respectively, which are large standardized effects. The magnitude of time effects and time-by-treatment arm interaction effects detectable with a .80 power will range from $.27$ to $.18$, also respectively, which are medium-sized standardized effects. Thus, the study is underpowered to detect any but large differences

between the treatment arms and medium-sized or larger effects on time and time-by-treatment arm interactions. More important than the statistical comparisons, though, the analyses will yield key descriptive characterizations of the treatment-arm effects at the two posttest points (i.e., means, medians, proportions, and variances) on key outcomes, as well as effect size estimates that can be used in planning a larger scaled efficacy trial of the PIE intervention.

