Objective 4. Determine the extent to which autonomic indices of infant self-regulation change over the course of the PIE intervention.

H4a: From Pretest to Posttest-2, infants will show limited changes in autonomic indices during exposure to nonsocial stimuli (Cohen's $d < .25$), but will show moderate-sized increases in respiratory sinus arrhythmia (RSA) and decreases in skin conductance levels (SCL) during exposure to child-directed speech (Cohen's $d \geq .40$).

H4b: Infants will demonstrate small improvements in language, sensory reactivity patterns, response to joint attention, and social-communication skills over the course of the PIE intervention.

Analyses: The models for these analyses will use the repeated measures mixed modeling framework, as for Objectives 1, 2 and 3, except that the effects will be examined only at Posttest-2 (given that these measures will not be taken at Posttest-1). The models will include terms for treatment arm effects and treatment arm-by-time interactions.

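### H4a predicts autonomic change specific to child-directed speech, but the Objective 4 models contain no stimulus-condition term, so the plan never tests whether the two changes differ

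*Combined protocol and SAP*

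**What the plan says.** Section 6.4.3.2 states H4a in two parts. The first is that "infants will show limited changes in autonomic indices during exposure to nonsocial stimuli", with d < .25. The second is a moderate rise in RSA and fall in SCL during child-directed speech, with d ≥ .40. Section 4.1 has the same hypothesis under Objective 4, where it is labelled H3b.

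Section 5.2.2 describes the RSA paradigm as infants "passively observing (a) an instrumental music video without social images, and (b) three on-minute vignettes of infant-directed speech". SCL is measured in the same paradigm, and section 6.1.3 places both measures in one procedure at Baseline and Posttest-2. The directional predictions under outcomes 4 and 5 concern speech only; for RSA, "We hypothesize we will see increased RSA levels during infant-directed speech". The Synopsis does not mention the nonsocial video.

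The Objective 4 analysis uses the repeated-measures mixed model of the other objectives, with effects examined at Posttest-2 only, and adds: "The models will include terms for treatment arm effects and treatment arm-by-time interactions". Sections 6.4.1 and 6.4.3 describe that framework as assessing time and treatment-order effects.

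**The concern.** H4a is a statement about a difference between two changes in the same infant. The stated model can estimate a change over time and whether it differs by arm. It cannot say whether the change under speech exceeds the change under the nonsocial video. Nothing in the plan says whether the nonsocial segment is modelled at all, or how the d < .25 limit is to be judged.

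This matters because every dyad receives the full intervention, and section 6.2.1 says the design lacks the controls needed for an efficacy evaluation. Infants are at least 16 weeks older at Posttest-2 than at Baseline (section 6.3.1). Anything that moves RSA or SCL in both conditions, such as maturation or familiarity with the laboratory and sensors, enters the speech change in full. The nonsocial video is the only within-infant reference recorded for these two outcomes, and it removes a shared shift only if the two changes are contrasted.

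**Working it through.** **The plan's own figures.** Section 6.4.2 is the source for sample size and correlation: "40 dyads (20 per treatment arm) will have complete data for analyses" and "Assuming a conventional type I error rate of .05, and intercorrelations among the repeated measures from .3 to .7". Its detectable effects reproduce from the noncentral F distribution with N = 40, two groups and m = 2 time points. The noncentrality is f²Nm/(1+(m−1)ρ) for arm and f²Nm/(1−ρ) for time and time-by-arm. At ρ = .3 and .7 this gives f = .366 and .419 for arm (stated .37 and .42), and .269 and .176 for time and interaction (stated .27 and .18). These figures are not in dispute, and none of them covers a contrast between stimulus conditions.

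**Inputs for the check.** From the documents: n = 40; Baseline to Posttest-2 correlation r = .5, the middle of the stated range; limits .25 and .40. Assumed, because the documents give no figure:
- an identical true shift s in both conditions (no speech-specific effect), in the predicted direction, s = .30 to .40 SD;
- a correlation q between the two conditions' changes of .3 to .7;
- d standardised by the raw-score SD.

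The SD of change is √(2(1−r)) = 1.00, so the SE of a mean change is 1/√40 = .158.

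**Three ways of reading the results under a shared shift.**

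(a) Only speech is analysed. P(observed d ≥ .40) = 1 − Φ((.40 − s)/.158):
- s = .30: 1 − Φ(.63) = 26%
- s = .35: 1 − Φ(.32) = 38%
- s = .40: 1 − Φ(0) = 50%

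(b) Each condition is tested separately (paired t, two-sided .05, by simulation). Speech is significant and nonsocial is not in 11% (s = .40, q = .7) to 20% (s = .30, q = .3) of trials.

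(c) Both H4a limits are applied to point estimates. P(speech d ≥ .40 and nonsocial d < .25), from the bivariate normal with correlation q:

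| s | q = .3 | q = .5 | q = .7 |
|---|---|---|---|
| .30 | 6.3% | 3.9% | 1.7% |
| .35 | 6.3% | 3.9% | 1.7% |
| .40 | 5.5% | 3.5% | 1.5% |

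**The direct contrast** (speech change minus nonsocial change). A shared shift cancels, so the error rate is 5% whatever s is. The 95% half-width for one condition is 2.024 × .158 = .32 SD (t, 38 df). For the contrast it is .32 × √(2(1−q)), which is .38, .32 and .25 SD at q = .3, .5 and .7.

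Power uses a noncentral t with noncentrality Δ√40/[√(2(1−r))·√(2(1−q))]. Over r = .3 to .7 and q = .3 to .8, it is about 10% to 47% for .40 versus .25 (Δ = .15) and about 42% to over 99% for .40 versus 0 (Δ = .40).

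**The case against.** The strongest reply is that H4a carries its own safeguard. A shift shared by both conditions tends to break the nonsocial limit. If both limits are applied as written, such a shift passes in only 1.5% to 6.3% of trials, close to the error rate of the proposed contrast. This stands. A reader might infer that a general age-related shift would pass as the predicted change; the documents do not support that. The larger percentages need the nonsocial segment to be left out, or a significant-versus-not rule that H4a does not state. The plan mandates neither. It also excludes neither, because it does not say how the two conditions are modelled or compared.

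It is also fair that the shift is hypothetical. The documents give no size for age-related change in RSA or SCL, and no direction. To mislead, it would have to raise RSA or lower SCL.

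Finally, these are two of eleven secondary outcomes in a proof-of-concept study. Section 6.4.2 ranks description above testing, and section 6.4.3 accepts extra type I error. That limits the weight of the point. It does not supply an analysis for the comparison that H4a makes, and the effect sizes are meant to inform a larger trial.

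**Conclusion.** The point holds as a gap in the analysis of a secondary hypothesis. H4a claims specificity, the data to examine it are collected, and the stated model does not compare the two conditions. A shared shift in the predicted direction could therefore be read as the predicted change. How often depends on an analysis rule that the plan leaves open: 26% to 50% if speech alone is analysed, 11% to 20% if separate significance tests are compared, and 1.5% to 6.3% if both point-estimate limits are applied. These figures rest on n = 40, r = .5, an assumed shared shift of .30 to .40 SD and q of .3 to .7.

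Nor should it be inferred that a condition contrast would establish an effect of the intervention. A speech-specific change could still be developmental, since there is no untreated control.

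**What to change.** In section 6.4.3.2, for RSA and SCL, enter both stimulus conditions in the mixed model with condition and time-by-condition terms. Name the time-by-condition contrast (speech change minus nonsocial change, Baseline to Posttest-2) as the test of specificity in H4a. Report both condition-specific changes with confidence intervals, and judge the nonsocial d < .25 limit from its interval. In section 5.2.2 and the Synopsis, define outcomes 4 and 5 in both conditions. An arm-by-time-by-condition term is optional, since no hypothesis calls for it.

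The change is wording only; both conditions are already recorded. The costs to state in the plan are these:
- The contrast's interval is wider than for one condition if q is below .5 (half-width .38 against .32 SD at q = .3).
- Its power for .40 versus .25 is low, about 10% to 47%, so a non-significant contrast would not refute H4a.
- With a half-width of .32 SD at r = .5, the nonsocial interval lies below .25 only if the estimate is below .25 − .32 = −.07. That limit will probably stay unresolved and should be reported so.
- The contrast does not separate the intervention from development.

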6.4.3.3 Analysis of Subject Characteristics

Baseline characteristics will be analyzed by study arm as follows:

1. Child age - corrected age in months - mean, SD, range
2. Child sex - male, female - numbers in each category
3. Child race, as identified by parents - White, Black, More than one race, Other - numbers in each category
4. Parent self-identified race - White, Black, More than one race, Other - numbers in each category
5. Child ethnicity, as identified by parents - Latino/Hispanic, Non-Latino/Non-Hispanic - numbers in each category
6. Parent self-identified ethnicity - Latino/Hispanic, Non-Latino/Non-Hispanic - numbers in each category
7. Parent education - level of education of parent enrolled in the study - numbers of parents with highest education level: < high school; completed high school; completed 1-2 year post high school certificate or degree program or some college; hold 4-year college degree (Bachelor's level); hold graduate or professional degree (Master's, PhD, MD, JD).
8. Child scores on the Mullen Scales of Early Learning - Visual Reception and Fine Motor T-scores - mean, SD, range
9. Child scores on the MacArthur Communication Development Inventory - words understood, words spoken, gestures - mean percentile score, SD, range
10. Parent Stress Scale - total scale score - mean, SD, range

For each of these baseline characteristics, comparisons will be made between dyads assigned to the two study arm to evaluate baseline equivalence of the arms on non-outcome characteristics.

6.4.3.4 Interim Analysis

We do not plan for interim analyses.

6.4.3.5 Health economic evaluation, if applicable

Not applicable.

6.4.3.6 Other

6.4.4 Subsets and Covariates

Models will initially be run without covariates. If any baseline characteristics differ significantly between the two study arms, we will consider rerunning models with covariates if there is a conceptual basis for the covariate potentially confounding the study outcomes.

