5.2.2 Secondary and Exploratory Outcome Variables

Secondary outcome variables:

The first three secondary outcome measures will be assessed at three timepoints: Baseline, Posttest 1 (after families have been randomly assigned to an intervention arm and coached in one of the two PIE intervention domains), and Posttest 2 (after families have been coached in both of the PIE intervention domains). For these measures, we are particularly interested in whether there are effects specific to the initial PIE coaching domain (sensory

reactivity or prelinguistic communication) at Posttest 1, and whether there are order effects (differences between study arms) at Posttest 2.

1. Changes in parent responsiveness to infant sensory reactivity cues. [Measured via a project-developed rating tool.] This secondary measure is included to determine whether coaching in the sensory reactivity domain yields the expected specific effects on parents' responses to infant sensory reactivity cues. Parents will be rated on a 1-7 scale for their responsiveness to sensory reactivity for each of the 4 activities included in the parent-infant interaction session, using videorecordings of these sessions. A manual will be developed to describe the rating system and the level of responsivity associated with each of the 7 points on the scale. Research assistants will be trained to reliability by supervising staff. During rating of the project videos, one of 5 rated videos will be independently rated for reliability. Raters will be blind to study arm and timepoint of participants.
2. Changes in parent responsiveness to infant prelinguistic communication cues. [Measured via a project-developed rating tool.] This secondary measure is included to determine whether coaching in the prelinguistic communication domain yields the expected specific effects on parents' responses to infant prelinguistic communication cues. Manualization, training and reliability procedures are identical to those described for the parent responsiveness to sensory reactivity measure.

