6.4 Statistical Method

6.4.1 Statistical Design

The study is designed as a randomized comparative trial with two phases. For Study Phase 1, dyads will participate in baseline assessments; then eligible, consenting families will be randomized, stratifying by child age, to one of two treatment arms. Arm1 families will participate in initial coaching on the PIE sensory reactivity (SR) domain, and Arm2 families will participate in initial coaching on the PIE prelinguistic communication (PC) domain. Families will participate in 6 weekly coaching sessions in their respective treatment arms, and return for Posttest-1. For Study Phase 2, dyads in Arm1 will receive 6 weekly coaching sessions on the PC domain, and dyads in Arm2 will receive 6 weekly coaching sessions on the SR domain. Then families will return for Posttest-2.

Comparisons of dyads assigned to Arm1 and Arm2 at Posttest-1 will allow us to estimate the separate effects of the two domains of PIE coaching, as dyads will have only been coached in one domain (responding to prelinguistic communication cues or sensory reactivity cues) prior to Posttest-1. At Posttest-2, we will get estimates of the additive effects of coaching in the second PIE domain, and be able to evaluate whether there are any effects of the order of coaching by comparing dyads in Arm1 to those in Arm2.

For analyses, we will utilize repeated measure analyses within a mixed modeling framework, to assess time and tx order effects, while accommodating missing data and optimally utilizing all available data.

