6.4.3.1 Primary Analyses

The primary objective of this study is to examine whether the novel PIE intervention transforms parent-infant transactions over time as intended, thereby facilitating increases in the time infants spend in dyadic engagement with their parents. We will also evaluate whether dyadic engagement outcomes differ based on whether parents are coached first in the sensory reactivity domain followed by coaching in the prelinguistic communication domain, or are coached in the opposite order.

Specifically, we will estimate the separate and combined effects of the two PIE intervention domains on dyadic engagement (primary outcome). H1a: At Posttest-1, dyads coached in either PIE domain will exhibit moderately more dyadic engagement compared to Baseline (Cohen's $d \geq .40$). H1b: At Posttest-2, dyads in both study arms will show additional small to moderate increases in dyadic engagement compared to Posttest-1 (Cohen's $d \geq .25$).

Our primary analysis will be conducted to explore a priori contrasts of interest within using repeated measures within a mixed modeling framework. Of key interest will be the contrast of Baseline to Posttest-1 scores and the contrast of Baseline to Posttest-2 scores (time effect). In addition, the model will include terms for treatment arm effects and treatment arm-by-time interactions. A time effect will indicate growth in the outcome from baseline to the posttest point, a zero or negligible time effect indicates stability, and a negative time effect suggests a drop in scores. A non-negligible treatment arm effect indicates that the two treatment arms differ on the outcome; while a non-negligible interaction coefficient suggests that the magnitude of change from baseline to the posttest point are not equivalent for members of the 2 treatment arms. Since the primary outcomes are proportions, arc sin transformations of these proportions will be performed before entering them into the models.

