6.4.3.2 Secondary Objectives Analyses, if applicable

Secondary Objective Analyses

Objective 2. Estimate the separate and combined effects of the two PIE intervention domains on infant intention communication.

H2a: At Posttest-1, infants in both groups will show no more than modest gains in intentional communication (Cohen's $d < .25$).

H2b: At Posttest-2, infants in both groups will show moderate increases in intentional communication compared to Baseline (Cohen's $d \geq .40$).

Analyses: This outcome variable involves counts of infant intentional communication attempts. We expect the average number of counts to be sufficiently large (eg. ≥ 8) that a normal approximation to a Poisson error distribution will be appropriate; however, if not, Poisson or negative binomial regression methods, or nonparametric approaches may be employed. The analyses for Objectives 2 and 3 will use the same framework as for our primary Objective #1, that is, to evaluate a priori contrasts of interest within a repeated measures mixed modeling framework. We will examine the contrast of Baseline to Posttest-1 scores and the contrast of Baseline to Posttest-2 scores (time effect). In addition, the models will include terms for treatment arm effects and treatment arm-by-time interactions.

Objective 3. Evaluate the differential changes in parent responsiveness following coaching on two individual Parents and Infants Engaged (PIE) intervention domains — responses to variable infant (a) sensory reactivity or (b) prelinguistic communication — as well as cumulative changes in parent responsiveness following coaching on both PIE domains.

H3a: At Posttest-1, parents in both intervention arm will show increases in responses attuned to their infants' behaviors compared to Baseline, with parents coached in the sensory reactivity domain showing more responses attuned to infants' sensory reactivity, and parents coached in the prelinguistic communication domain showing more responses attuned to infants' signals of attention focus and communicative intent.

H3b: At Posttest-2 (after coaching in both PIE domains), there will be no between-arm differences in parent responses attuned to infant sensory reactions or prelinguistic communication leads, due to increases in parent responsiveness to the newly coached domain of infant behaviors.

Analyses: See analyses for Objective 2.

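### The arm comparisons have no prespecified adjustment for baseline score or age stratum, and the plan does not choose between a difference in change and a difference at posttest

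*Combined protocol and SAP*

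**What the plan says.** **Model terms.** Sections 6.4.3.1 and 6.4.3.2 plan repeated-measures mixed models with time, arm and arm-by-time. For Objective 4: "The models will include terms for treatment arm effects and treatment arm-by-time interactions". Baseline is one of the repeated responses. No section sets a common baseline mean or makes the baseline score a covariate.

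**Covariates.** Section 6.4.4: "Models will initially be run without covariates". If a baseline characteristic differs significantly between arms, a rerun with covariates will be considered, "if there is a conceptual basis for the covariate potentially confounding the study outcomes". The baseline comparison in 6.4.3.3 is confined to non-outcome characteristics; it lists child age but not the baseline outcome scores. Section 6.4.3 allows a post-hoc covariate for number of sessions, and 6.4.5 mentions covariates related to missingness.

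**Stratum.** Sections 5.1 and 6.1.2 stratify randomisation at 14 months of age. No analysis section includes the stratum.

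**Arm contrast.** Section 6.4.3.1 reads the interaction as showing that "the magnitude of change from baseline to the posttest point are not equivalent for members of the 2 treatment arms". It also describes an arm effect without naming a visit. Elsewhere the contrast is cross-sectional: "Comparisons of dyads assigned to Arm1 and Arm2 at Posttest-1 will allow us to estimate the separate effects of the two domains" (6.4.1); "and whether there are order effects (differences between study arms) at Posttest 2" (5.2.2); and H3b, that "there will be no between-arm differences in parent responses attuned to infant sensory reactions or prelinguistic communication leads" (6.4.3.2).

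**The concern.** The point concerns only the arm comparisons: the domain contrast at Posttest-1, the order contrast at Posttest-2, and H3a and H3b. The Baseline-to-posttest time contrasts behind H1a and H1b, which 6.4.3.1 treats as the main interest, are not affected.

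The arm comparisons are the only randomised comparisons in the trial, and the order question is part of the primary objective. Section 6.4.2 puts descriptive arm effects at the two posttests, and effect sizes for a later trial, above the significance tests. Estimates of that kind need a defined contrast and the narrowest interval the data allow.

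With a free baseline mean in each arm and complete data, the planned model yields either the difference in change or the raw posttest difference. Which of these is more precise depends on the baseline-to-posttest correlation. With equal SDs the order reverses at .5, inside the protocol's own range, so a good choice between them cannot be made in advance. Leaving the choice open also allows it to be made after the data are seen.

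**Working it through.** **Inputs.** From 6.4.2: N = 40 (20 per arm), type I error .05, 80% power, correlation r from .3 to .7. Assumptions: two-sided tests, complete data, one common correlation. The documents give no SDs, so results are in posttest-SD units, and k is the assumed ratio of posttest SD to baseline SD.

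**1. The plan's own figures.** For 80% power, F(1,38) needs noncentrality 8.265. With two occasions (N × 2 = 80):

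- Arm effect: f = √(8.265 × (1 + r)/80) = .366 at r = .3 and .419 at r = .7. The plan states .37 to .42.
- Time and interaction: f = √(8.265 × (1 − r)/80) = .269 and .176. The plan states .27 to .18.

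Both reproduce. With three occasions the arm values would be .332 and .407, which do not match. For two arms and two occasions, the arm difference in change equals 4f: 4 × .269 = 1.08 SD and 4 × .176 = 0.70 SD.

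**2. Variance of the arm difference.**

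- Difference in change: (1 + 1/k² − 2r/k) × 4/40. At k = 1 this is 2(1 − r) × 0.1.
- Posttest difference: 4/40 = 0.1.
- Baseline-adjusted: (1 − r²) × 4/40 × (1 + 1/36). The last factor is the cost of estimating the slope.

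At k = 1, 2(1 − r) = 1 when r = .5, which is where the two unadjusted contrasts change order.

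**3. Equal SDs (k = 1).** The detectable difference is √(noncentrality × variance), with 8.265 on 38 df (unadjusted) or 8.277 on 37 df (adjusted). The half-width is t(.975) × SE.

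| | r = .3 | r = .5 | r = .7 |
|---|---|---|---|
| Variance: change | .140 | .100 | .060 |
| Variance: posttest | .100 | .100 | .100 |
| Variance: adjusted | .0935 | .0771 | .0524 |
| Cut against change | 33% | 23% | 13% |
| Cut against posttest | 6% | 23% | 48% |
| 95% half-width, change / posttest / adjusted (SD) | 0.76 / 0.64 / 0.62 | 0.64 / 0.64 / 0.56 | 0.50 / 0.64 / 0.46 |
| Detectable, change / posttest / adjusted (SD) | 1.08 / 0.91 / 0.88 | 0.91 / 0.91 / 0.80 | 0.70 / 0.91 / 0.66 |
| Power at a true 0.8 SD, change / posttest / adjusted | 55 / 69 / 72% | 69 / 69 / 80% | 89 / 69 / 93% |

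A simulation of 40,000 trials with 20 per arm gave cuts of 34/23/12% against change and 6/23/48% against posttest.

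**4. Posttest SD larger than baseline SD.** The cut against the posttest difference does not depend on k.

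| k | Cut against change, r = .3/.5/.7 | Cut against the better unadjusted contrast |
|---|---|---|
| 1 | 33 / 23 / 13% | 6 / 23 / 13% |
| 1.25 | 19 / 8 / −1% | 6 / 8 / −1% |
| 1.5 | 10 / 1 / −3% | 6 / 1 / −3% |

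**5. Age stratum.** The documents give no association between age and outcome, so this part rests wholly on assumption. In a simulation (4,000 runs, 10 per arm per stratum, baseline-adjusted model, true difference 0.8 SD), adding the stratum raised power by 0.5 to 1.6 points if age correlates .3 with the outcome at both visits and by 0.9 to 6.2 points at .5, and left it essentially unchanged at 0. Each power value has a standard error of about √(.8 × .2/4000) = 0.6 points, so the smaller gains are only indicative.

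**The case against.** The strongest reply is that little depends on this. The main hypotheses concern change within dyads, section 6.2.1 disclaims an efficacy evaluation, and 6.4.2 already concedes that only large arm differences are detectable. This stands, and it limits the point to precision. It does not remove it, because these are the only contrasts that randomisation supports, and a small sample is a reason to use the data already collected.

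The largest gains are also best cases. The 48% requires r = .7 and the less precise of the two unadjusted contrasts. Equal SDs may not hold: Mullen language and Sensory Processing Assessment scores are selected by eligibility at baseline, which may narrow their spread. For intentional communication the plan expects that "a normal approximation to a Poisson error distribution will be appropriate"; near-Poisson counts become more variable as they rise. Step 4 covers this: the gain over the better unadjusted contrast can be small, but the loss stays at about 3%.

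It can be said that 6.4.3.1 settles the contrast through the interaction. It does define unequal change, but 5.2.2, 6.4.1 and H3b describe posttest differences, and nothing says which is to be reported. Child age could enter through 6.4.4, but only after a significant imbalance, which is not a prespecified stratum term. That age may not be prognostic is accepted.

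Finally, a model with baseline as covariate cannot also give the planned time contrasts. That is correct. A common baseline mean avoids it, because baseline remains a response.

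**Conclusion.** The point holds. Neither the baseline outcome score nor the age stratum is a prespecified adjustment of the arm contrasts, and the plan describes two arm contrasts without choosing one. Nothing is biased, and the pooled time contrasts are untouched.

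Over r = .3 to .7 and SD ratios of 1 to 1.5, baseline adjustment saves up to 48% of the variance and costs at most about 3%. In the equal-SD case it gives the smallest variance of the three at every r, and it removes the need to guess which unadjusted contrast will do better. The result rests on complete data from 40 dyads and assumed SD ratios. The benefit of the stratum term cannot be determined from the documents. Even when adjusted, the detectable difference is 0.88 to 0.66 SD with equal SDs, so small sample size remains the main limit.

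**What to change.** In 6.4.3.1, 6.4.3.2 and 6.4.4:

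- Name the arm difference at Posttest-1 and the arm difference at Posttest-2 as the arm contrasts (Posttest-2 only for outcomes not analysed at Posttest-1).
- Estimate them on each outcome's analysis scale from a model with a common Baseline mean for both arms. This stays within the planned mixed model and full-information likelihood and keeps the time contrasts. Baseline score as covariate is the alternative for the arm contrasts.
- Include the age stratum (below 14 months versus 14 months or older) as a prespecified fixed effect.
- Describe baseline characteristics by arm, but do not let significance tests of them decide on adjustment.

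Optionally, note in 6.4.2 that the f values correspond to two occasions and that the interaction values equal an arm difference in change of 1.08 to 0.70 SD. The f values themselves need no correction.

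The cost is SAP wording and one or two degrees of freedom, with no new data. If the posttest SD is well above the baseline SD and r is near .7, adjustment gives up about 1 to 3% in variance relative to the difference in change.
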